#### 7.4 Methods and timing for assessing, recording and analysing variables

Appendix 24.1 presents the study schedule with timing (Flowchart). The assessment methods with instructions are described in detail under chapter 11.

Informed consent shall be obtained in writing from the patient or patient's legally authorized representative and the process shall be documented before any procedure specific to the study is applied to the patient. Informed consent may be given by the legally authorized representative only if a patient is unable to make the decision to participate in the study (e.g. seriously ill or unconscious patient, mentally ill person, mentally handicapped person). In such cases, the patient shall also be informed about the study within his/her ability to understand.

Study Schedule: Day 01

1. Review the inclusion and exclusion criteria
2. Randomize the patient to the allocation group (3M study device or hospital IAD standard care)
3. Complete patient demographics (gender, age, height, weight, main reason for hospitalization)
4. Record IAD history (date of IAD diagnosis if known, IAD status, IAD occurrence first/recurrent, incontinence type, comorbidities)
5. Obtain current concomitant medication
6. Capture information with regard to the Barthel Index
7. Complete the Braden Scale for Predicting Pressure Sore Risk
8. Perform skin cleansing
9. Ask the patient to indicate the IAD pain level before and during cleansing using the Wong-Baker FACES® Pain Rating Scale (assessment only for cognitively healthy patients according to the judgement of the study nurse)
10. Perform a structured IAD skin assessment according to the GLOBIAD Tool. Estimate the IAD affected area in cm^2 using the measurement sheet provided by the sponsor (either of the total affected IAD area inclusive signs of erythema or with focus on skin loss only). Fill out the IAD study diary with regard to skin assessment information.

 
3M Deutschland GmbH [name] [name], Germany
	
Clinical Investigational Plan / Protocol
 
3M Confidential
	
CLIN-PROT-EU-05-293312 Version: 3 Status: Release Release Date: 01/30/2018 07:29:52 AM CST Page 26 of 60

--	--	---

11. Take photographs of the study area according to the site procedure manual. Upload the photographs into the photo database.
12. Depending on the randomization allocation apply Cavilon Advanced Skin Protectant or the IAD hospital standard care product
13. Ask the patient to indicate the IAD pain level before, during and after the application of Cavilon Advanced Skin Protectant or the IAD hospital standard care product using the Wong-Baker FACES® Pain Rating Scale (assessment only for cognitively healthy patients according to the judgement of the study nurse). Document observations regarding weeping/exuding and bleeding after product application.
14. Track IAD care information over the day/night and fill out the IAD study diary (incontinence status, use of urinary catheter, use of fecal management system, frequency of absorbent pad or diaper changes, frequency of intimate cleansing procedures, application frequency of IAD care products, IAD specialist appointments/visits)
15. Capture detailed information with regard to the use of certain IAD care products in the study such as cleansing products, skin protectants building up the moisture barrier, IAD wound dressings or other products if applicable [product name, treatment duration period, product type, manufacturer, REF number (indicates the manufacturer's catalogue number so that the medical device can be identified), packaging unit, number of containments used for the study]
16. Record adverse events, if applicable
17. Record protocol deviations, if applicable

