## 7.2 Randomization and blinding

The random numbers will be generated by computer. The randomization is stratified with respect to two different IAD severity categories according to the Ghent Global IAD Categorization Tool [33; appendix 24.2]. Stratum 1 is defined as IAD category 1A (persistent redness without clinical signs of infection) and Stratum 2 as IAD category 2A (skin loss without clinical signs of infection). The strata are of same sizes (50:50 ratio). The participants will receive either Cavilon Advanced Skin Protectant or the local hospital IAD care products within the same stratum. Due to the obvious differences between the comparative hospital IAD care products and the study device, the study nurses cannot be blinded. A blinded assessor will assess the healing outcome based on the photographs of the study area that is defined as the sacral region going down to the upper thighs, bordered approximately 5 cm below the gluteal fold.

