6. Depending on the randomization allocation apply Cavilon Advanced Skin Protectant (Day 04, Day 07, Day 10, Day 13, Day 16, Day 19) or the IAD hospital standard care product following the hospital medical routine/interval
7. Day 04, Day 07, Day 10, Day 13, Day 16, Day 19 (+/- 1 day):  
Ask the patient to indicate the IAD pain level before, during and after the application of Cavilon Advanced Skin Protectant or the IAD hospital standard care product using the Wong-Baker FACES® Pain Rating Scale (assessment only for cognitively healthy patients according to the judgement of the study nurse).\_Document observations regarding weeping/exuding and bleeding after product application.
8. Track IAD care information over the day/night and fill out the IAD study diary (incontinence status, use of urinary catheter, use of fecal management system, frequency of absorbent pad or diaper changes, frequency of intimate cleansing procedures, application frequency of IAD care products, IAD specialist appointments/visits)
9. Capture detailed information with regard to the use of certain IAD care products such as cleansing products, skin protectants building up the moisture barrier, IAD wound dressings or other products if applicable [product name, treatment duration period, product type, manufacturer, REF number (indicates the manufacturer's catalogue number so that the medical device can be identified), packaging unit, number of containments used for the study]

 
3M Deutschland GmbH [name] [name], Germany
	
Clinical Investigational Plan / Protocol
 
3M Confidential
	
CLIN-PROT-EU-05-293312 Version: 3 Status: Release Release Date: 01/30/2018 07:29:52 AM CST Page 28 of 60

--	--	---

10. Record adverse events if applicable
11. Record protocol deviations if applicable

NOTE: Any recurrence of IAD in both study groups is to be examined. If the hospital routinely does not use IAD prevention products, the recurrence of IAD is still to be observed for the group allocated to hospital IAD standard care. In this case, the study procedures of “Application: Comparator” and “Pain Score: Application” no longer apply (Appendix 24.1 B).

Study Schedule: End of Study (Day 21 or discontinuation)

1. Perform skin cleansing

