(only for cognitively healthy patients according to the judgement of the study nurse)

- ✓ IAD pain scores according to the Wong-Baker FACES® Pain Rating Scale at the start and the end of the study (pain scores 0 – 10)
- ✓ Pain scores according to the Wong-Baker FACES® Pain Rating Scale associated with the incontinence cleanup (pain scores 0 – 10)
- ✓ Pain scores according to the Wong-Baker FACES® Pain Rating Scale associated with the IAD product application (pain scores 0 – 10)

Material cost and resource use

- ✓ Material cost based on the information with regard to the utilization of certain IAD care products such as cleansing products, skin protectants building up the moisture barrier, IAD wound dressings or other products, their used quantity, application frequency and duration of use.
- ✓ Resources involved in the IAD therapy (e.g. number of nurses or specialists/ number of interventions)

IAD Nursing Time

- ✓ Time taken to clean up incontinence in minutes
- ✓ Time taken to apply the skin protectant building up the moisture barrier and other products that might be needed to prepare the skin ( e.g. lotions to dry-out lesions before applying the skin protectant building up the moisture barrier)

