**11.2 Assessment method**

Barthel Index [26]

The Barthel Index will be completed at the start of the study to characterize the patients with regard to their degree of independence in activities of daily living. The evaluation addresses 10 items: help needed with feeding, help needed with transfers e.g. from chair to bed, help needed with grooming, help needed with toilet use, help needed with bathing, help needed

 3M Deutschland GmbH [name] [name], Germany	Clinical Investigational Plan / Protocol  3M Confidential	CLIN-PROT-EU-05-293312 Version: 3 Status: Release Release Date: 01/30/2018 07:29:52 AM CST Page 36 of 60
--	---	---

with walking, help needed with climbing stairs, help needed with dressing, presence or absence of fecal incontinence and presence or absence of urinary incontinence. The possible scores range from 0 – 100, with lower score indicating increased disability.

Braden Scale for Predicting Pressure Sore Risk [29, 30]

The Braden Scale will be completed at the start of the study to assess the patient’s level of risk for development of pressure ulcers. The evaluation is based on six indicators: sensory perception, moisture, activity, mobility, nutrition, and friction or shear. Total possible scores range from 6-23, with lower score indicating a higher risk of developing a pressure ulcer.

Wong-Baker FACES® Pain Rating Scale [31]

This pain assessment tool was originally created with children for children to help them communicate about their pain. Faces with different expressions from smiling to crying facilitate the communication as anchor for pain intensity scale 0 – 10, with higher score indicating more pain. The nurses will ask the patients to choose the face that best depicts the pain they are experiencing. Only cognitively healthy patients according to the judgement of the study nurse will be asked. The IAD pain scores will be assessed before and during cleansing following the local hospital cleansing procedure. In addition the IAD pain scores will be measured before, during and after application of the skin protectant building up the moisture barrier.

Pain assessment instructions (not valid for patients with reduced consciousness or dementia)

1. Explain to the patient that each face represents a person who has no pain (hurt), or some, or a lot of pain

Figure 1: © 1983 Wong-Baker FACES Foundation. www.WongBakerFACES.org. Used with permission

3M Deutschland GmbH  
[name]  

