**24.1 Clinical investigational schedule**

**A) Patients allocated to Cavilon Advanced Skin Protectant**

Assessment	IC	D01	D02	D03	D04	D05	D06	D07	D08	D09	D10	D11	D12	D13	D14	D15	D16	D17	D18	D19	D20	End of Study (D21 or discontinuation)
Informed Consent (IC)	X																					
Inclusion/Exclusion		X																				
Randomization		X																				
Demographics		X																				
IAD History		X																				
Medications		X																				
Barthel Index		X																				
Braden Scale		X																				
Skin Cleansing		X	X	X	X	X	X	X	X	X	X	X	X	X	X	X	X	X	X	X	X	X
Pain Score: Cleansing		X			X			X			X			X			X			X		X
IAD Nursing Time					X																	
Skin Assessment (Diary)		X	X	X	X	X	X	X	X	X	X	X	X	X	X	X	X	X	X	X	X	X
Photography		X			X			X			X			X			X			X		X
Application: Study Device		X			X			X			X			X			X			X		
Pain Score: Application		X			X			X			X			X			X			X		
Tracking IAD Care (Diary)		X	X	X	X	X	X	X	X	X	X	X	X	X	X	X	X	X	X	X	X	X
IAD Product Specification		X	(X)																			
Adverse Events		(X)																				
Protocol Deviation		(X)																				
End of Study Form																						X

(x) = if applicable

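### Day 01 lists randomisation before the unblinded study nurse judges who can be pain-scored and takes baseline cleansing pain, and nothing requires those records before the arm is known

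*Combined protocol and SAP*

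**What the plan says.** All references are to the protocol.

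- **Order of Day 01 (7.4).** Item 2 reads "Randomize the patient to the allocation group (3M study device or hospital IAD standard care". Cleansing is item 8. Pain before and during cleansing is item 9, limited by the words "assessment only for cognitively healthy patients according to the judgement of the study nurse". The GLOBIAD assessment with area estimate is item 10, photographs are item 11, and product application is item 12.
- **Blinding (7.2).** Of the staff who do this, it says "the study nurses cannot be blinded". The blinded assessor judges healing from photographs.
- **Who can be scored (11.2).** The instructions add "Pain assessment instructions (not valid for patients with reduced consciousness or dementia". They give no instrument, no cut-off and no point in time for the judgement. The patient gives the score: "The nurses will ask the patients to choose the face that best depicts the pain they are experiencing".
- **Status of pain.** It is endpoint 10 of eleven unranked endpoints (7.3). Section 11.1 lists as an effect parameter the score on the "Pain Rating Scale at the start and the end of the study".
- **Later occasions.** Application pain is repeated on "Day 04, Day 07, Day 10, Day 13, Day 16, Day 19 (+/- 1 day"). The row "Pain Score: Cleansing" in Appendix 24.1 also includes the end of study.
- **Analysis sets (6.1).** A full/safety set and a per-protocol set are defined. No pain set is.
- **Stratification.** The synopsis and 7.2 name IAD category only. The synopsis, 6.2 and 9.7 expect five patients per arm in each category at each site.

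**The concern.** Randomisation makes the arms comparable as allocated. It does not protect a comparison whose members are chosen afterwards by someone who knows the arm. Pain is scored only in patients whom the nurse judges cognitively able. If that judgement is first made at item 9, after allocation at item 2, the pain data of the two arms could come from differently selected patients. The baseline against which later pain is read would also be taken with the arm known.

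For skin category and affected area, Day 01 photographs go to the blinded reader (synopsis and 11.2), so healing has an independent baseline. Pain has none. The study is meant to inform the feasibility of a confirmatory trial (5.1), so a distorted pain difference could carry forward into that planning.

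**Working it through.** **1. Is the listed order binding?**

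- Item 9 asks for pain before the cleansing that is item 8, so the list is not strictly chronological.
- IAD category is an inclusion criterion (9.1) and the stratification factor (7.2). It must be known before item 2, although the structured assessment is item 10.
- Appendix 24.1 A and B show only that these steps fall on D01.

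The order is therefore not fixed. No section requires the pain judgement or the baseline cleansing scores before allocation, and none conceals the arm at item 9.

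**2. Is there a blinded check on pain?**

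The central reader's tasks in 11.2 are category and traced area from photographs. Neither bears on pain scores or on who is scored.

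**3. How much of the schedule does reordering reach?**

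Inputs are from 7.4 and Appendix 24.1.

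- Cleansing pain: D01, 04, 07, 10, 13, 16, 19 and end of study = 8 occasions × 2 ratings (before, during) = 16.
- Application pain: D01, 04, 07, 10, 13, 16, 19 = 7 occasions × 3 ratings (before, during, after) = 21.
- Maximum per patient: 8 + 7 = 15 occasions and 16 + 21 = 37 ratings.
- Moved ahead of allocation by the fix: the two Day 01 cleansing ratings. The other 37 − 2 = 35 still follow it, including the rating just before first application (item 13).

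These counts describe the schedule. They do not measure bias.

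**4. Can the bias be sized?**

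Not from the documents. They give neither the share of patients who can be scored nor any error rate for the judgement. Purely for scale, suppose k patients are left out of one arm's n scorable patients and they score d points above the rest. That arm's mean then shifts by k × d / n. Assume k = 2, d = 4 and 25% to 75% of 30 patients scorable:

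- 2 × 4 / 7.5 = 1.07 points on the 0–10 scale
- 2 × 4 / 22.5 = 0.36 points

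All of these inputs are assumptions.

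**5. Secondary: the per-site split.**

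The plan's total reproduces: 3 sites × 2 categories × 2 arms × 5 = 60. Now assume one 15:15 list per category and exactly 10 patients per site and category; the documents do not state the list structure.

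- All three sites 5:5 in one category: C(10,5)³ / C(30,15) = 252³ / 155,117,520 = 0.1032. In both categories: 0.1032² = 0.0106, about 1.1%.
- No cell worse than 6:4 in one category: (252³ + 6 × 210 × 252 × 210) / 155,117,520 = 82,682,208 / 155,117,520 = 0.533. At least one of six cells 7:3 or worse: 1 − 0.533² = 0.716.

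Category-only stratification is thus unlikely to deliver the expected split everywhere.

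**The case against.** The strongest reply is that this rests on the numbering of a list that is not a strict sequence, and that no section says the nurse knows the arm at item 9. Safeguards also exist:

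- 11.2 rules out impaired consciousness and dementia.
- The patient picks the face.
- A related judgement of capacity is made at consent, before any study procedure (7.4 and 17).
- Day 01 cleansing follows local procedure, with no arm-specific cleansing described.
- The trial is exploratory and descriptive, and pain is one of eleven endpoints.

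All of this stands, and it limits the point. It does not answer it: the safe order is neither required nor recorded, and capacity to consent is not the same judgement as fitness for pain scoring.

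A reader might infer more than the documents support:

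- **That an arm-aware judgement is made afresh at every pain occasion.** The restriction is repeated at later visits, but it can equally be read as one patient-level limit on the endpoint's population. No section prescribes a new judgement each time.
- **That fixing eligibility early secures the later ratings.** It fixes eligibility, not who is rated. Discharge ends follow-up (9.6). After healing, comparator application pain scoring stops where the hospital uses no prevention products (7.4, 9.6 and the note in section 24), while device application continues.
- **That the per-site figures contradict the randomisation.** They are stated as expectations and agree with 1:1 on average. A departure is chance noise, not bias.

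**Conclusion.** The point holds in a limited form. Followed as listed, Day 01 lets an unblinded nurse decide entry to the pain data and take baseline cleansing pain after allocation. Nothing in the protocol prevents this and no blinded check covers it. It concerns endpoint 10 only; the blinded healing assessment is unaffected. The documents do not show that bias will occur and give no basis for its size. The change is justified because the exposure is avoidable at almost no cost.

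The per-site split does not carry this conclusion. Its figures (about 1.1% and 71.6%) rest on the assumed list structure and cell sizes. Their only consequence is that the numbers should be labelled for what they are.

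**What to change.** **Main change.**

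- In 7.4, place randomisation after Day 01 item 11 and before item 12.
- Record the pain-eligibility judgement before allocation, using the criterion already in 11.2.
- Let that record define the main pain analysis set.
- Document any later change in assessability with date and reason, and report patients who become assessable later separately.
- State plainly that later ratings remain unblinded, and that missing pain scores after discharge or after comparator scoring stops need separate handling. This change does not address them.

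Cost: reordered steps and one recorded judgement, with no added patients, visits or procedures. The small downside is that patients who become assessable after Day 01 fall outside the main pain set.

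**Optional.** Label the five per arm at each site as expectations in the synopsis, 6.2 and 9.7. Do not add site-level blocks for this purpose, because in an open trial they make allocation easier to guess. Account for IAD category, the stratification factor, when estimating arm differences. Neither step costs anything in conduct.

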**Study Schedule: Day 02 – Day 20**

1. Perform skin cleansing
2. Day 04, Day 07, Day 10, Day 13, Day 16, Day 19, End of Study (discontinuation):  
Ask the patient to indicate the IAD pain level before and during cleansing using the Wong-Baker FACES® Pain Rating Scale (assessment only for cognitively healthy patients according to the judgement of the study nurse).
3. Day 04 IAD Nursing Time: Measure the time taken to clean up incontinence (front/back) and the time taken to administer the IAD treatment products to the study area that is defined as the sacral region going down to the upper thighs, bordered approximately 5 cm below the gluteal fold (patients assigned to Cavilon Advanced Skin Protectant and patients assigned to the local hospital IAD care regime). Please consider the nursing time measurement instructions (stopwatch and scale provided by the sponsor). Measure the

 3M Deutschland GmbH [name] [name], Germany	Clinical Investigational Plan /  Protocol  3M Confidential	CLIN-PROT-EU-05-293312 Version: 3 Status: Release Release Date: 01/30/2018 07:29:52 AM CST Page 27 of 60
--	--	---

weight of the skin protectant building up the moisture barrier before and after application if the patient is assigned to the local hospital IAD care regime group.

4. Perform a structured IAD skin assessment according to the GLOBIAD Tool. Estimate the IAD affected area in cm^2 using the measurement sheet provided by the sponsor (either of the total affected IAD area inclusive signs of erythema or with focus on skin loss only). Fill out the IAD study diary with regard to skin assessment information.
5. Photographs should be taken on Day 04, 07, 10, 13, 16, 19 and End of Study (Day 21 or discontinuation). Additional photos should also be taken at the first day no evidence of IAD is present (e.g. no erythema, no skin damage), i.e. transition from IAD1 to IAD free. If a patient has IAD 2 skin lesions/skin loss, additional photos should be taken on the first day of 100% re-epithelialization, i.e. IAD2 transition to IAD 1. Photographs must be taken according to the site procedure manual. Photos must be uploaded into the database if they refer to a study endpoint – either Day 01, Day 21, IAD2 to IAD1 or IAD1 to IAD free. Photos should be kept on the respective SD memory cards, labelled according to the site procedure manual and stored in the IAD study diary.
6. Depending on the randomization allocation apply Cavilon Advanced Skin Protectant (Day 04, Day 07, Day 10, Day 13, Day 16, Day 19) or the IAD hospital standard care product following the hospital medical routine/interval
7. Day 04, Day 07, Day 10, Day 13, Day 16, Day 19 (+/- 1 day):  
Ask the patient to indicate the IAD pain level before, during and after the application of Cavilon Advanced Skin Protectant or the IAD hospital standard care product using the Wong-Baker FACES® Pain Rating Scale (assessment only for cognitively healthy patients according to the judgement of the study nurse).\_Document observations regarding weeping/exuding and bleeding after product application.
8. Track IAD care information over the day/night and fill out the IAD study diary (incontinence status, use of urinary catheter, use of fecal management system, frequency of absorbent pad or diaper changes, frequency of intimate cleansing procedures, application frequency of IAD care products, IAD specialist appointments/visits)
9. Capture detailed information with regard to the use of certain IAD care products such as cleansing products, skin protectants building up the moisture barrier, IAD wound dressings or other products if applicable [product name, treatment duration period, product type, manufacturer, REF number (indicates the manufacturer's catalogue number so that the medical device can be identified), packaging unit, number of containments used for the study]

 
3M Deutschland GmbH [name] [name], Germany
	
Clinical Investigational Plan / Protocol
 
3M Confidential
	
CLIN-PROT-EU-05-293312 Version: 3 Status: Release Release Date: 01/30/2018 07:29:52 AM CST Page 28 of 60

--	--	---

10. Record adverse events if applicable
11. Record protocol deviations if applicable

NOTE: Any recurrence of IAD in both study groups is to be examined. If the hospital routinely does not use IAD prevention products, the recurrence of IAD is still to be observed for the group allocated to hospital IAD standard care. In this case, the study procedures of “Application: Comparator” and “Pain Score: Application” no longer apply (Appendix 24.1 B).

Study Schedule: End of Study (Day 21 or discontinuation)

1. Perform skin cleansing
2. Ask the patient to indicate the IAD pain level before and during cleansing using the Wong-Baker FACES® Pain Rating Scale (assessment only for cognitively healthy patients according to the judgement of the study nurse).
3. Perform a structured IAD skin assessment according to the GLOBIAD Tool. Estimate the IAD affected area in cm^2 using the measurement sheet provided by the sponsor (either of the total affected IAD area inclusive signs of erythema or with focus on skin loss only). Fill out the IAD study diary with regard to the skin assessment information.
4. Take photographs of the study area according to the site procedure manual. Upload the end of study photos into the photo database.
5. Track IAD care information and fill out the IAD study diary (incontinence status, use of urinary catheter, use of fecal management system, frequency of absorbent pad or diaper changes, frequency of intimate cleansing procedures, IAD specialist appointments/visits). Collect the IAD study diary at the end of the study.
6. Check the completeness of the information with regard to the use of certain IAD care products at the end of the study
7. Record adverse events if applicable
8. Record protocol deviations if applicable

